4 STUDY DESIGN

4.1 OVERALL DESIGN

We will use a Hybrid trial Type 1 effectiveness implementation study design⁷⁷ and a mixed methods approach to compare the effectiveness of culturally adapted-Somryst (+ usual care and a sleep hygiene brochure) vs. minimally enhanced usual care (mEUC; usual care plus sleep hygiene brochure). This is a parallel-group, single-site, 2-arm study.

Patients will be recruited through flyers, email, telephone, and primary care provider referrals from primary care clinics affiliated with Ambulatory Care Network (ACN) of New York Presbyterian Hospital (NYPH). The catchment areas are the ACN clinics of NYPH, which serve 1.4 million individuals in NYC, including low socioeconomic and racially/ethnically diverse communities in NYC such as Washington Heights, Inwood, Harlem, and the Southwest Bronx (31% African American; 61% Hispanic descent), as well as geographically broader communities, including Queens (11% African American; 25% Hispanic; 11% Asian/Pacific Islander).

We will enroll 200 adults who screen positive for chronic insomnia into an RCT that will compare the effectiveness the culturally-adapted digital CBT-I (Somryst) program versus minimally enhanced usual care (mEUC). Participants in the intervention arm will receive digital CBT-I, usual care by their PCP and a sleep hygiene brochure. Patients in the intervention group will also be trained on how to record their daily sleep diaries using a smartphone and will receive prompts on their smartphones or emails to remind them when to complete the daily sleep diaries. Patients randomized to the comparator group will receive minimally enhanced usual care, which will include usual care by their PCP and a sleep hygiene brochure. Patients in both groups will have their insomnia severity assessed again at post-intervention (9 weeks) and 6 months post-treatment. Patients in both groups will also wear the Actiwatch to objectively assess sleep for 2 weeks before randomization and again for the 2 weeks preceding the post-intervention assessment.

4.2 SCIENTIFIC RATIONALE FOR STUDY DESIGN

This is a single-site, parallel-group, 2-arm superiority randomized controlled trial of digital CBT-I (Somryst + usual care + sleep hygiene brochure) vs. minimally enhanced usual care (mEUC). Patients randomized

18 May 2022

to the minimally EUC condition will continue to receive the typical standard of care in that clinic from their primary care provider (which may include pharmacotherapy). We have labeled the condition "minimally enhanced" because participants will be provided with a sleep hygiene brochure. Minimally EUC was chosen as the comparator because it is of high clinical relevance, will allow us to determine if the adapted digital CBT-I is superior to usual care, and addresses ethical issues (i.e., identifying but not treating insomnia).⁷⁸

4.3 JUSTIFICATION FOR INTERVENTION

The digital CBT-I program used in this intervention (Somryst) is based off SHUTi, an interactive and tailored English-language web-based program modeled on the primary tenets of face-to-face CBT-I shown to be effective at reducing insomnia symptoms.²⁶ Participants will be asked to complete six cores (main intervention content) during the 9-week intervention period (a new Core becomes available 7 days after completion of the previous one). After completing a Core, they can review that Core at any time, and access program worksheets from the My Stuff section of the mobile program. The six cores are based on the primary treatment components provided in face-to-face cognitive behavioral therapy for insomnia.^{6,14} In order to expand access to the gold standard behavioral treatment for insomnia, adaptations of CBT-I to other languages and cultural contexts is necessary. The digital CBT-I (Somryst) has been adapted using a rigorous cultural adaptation framework. We used Barrera et al.'s cultural adaptation framework⁷⁹ to conduct formative qualitative research (N=18) and one-on-one personal interviews (N=13) with Spanishspeaking Latinx adults from the NYC region with chronic insomnia about digital cognitive behavioral therapy for insomnia for funded hybrid Type 1 effectiveness-implementation R01 trial (HS024274). As part of this process, participant input and feedback about sleep hygiene guidelines and ways in which these guidelines could be adapted for their urban context was obtained. Participants identified the need for key deep-level content changes to traditional sleep hygiene education, including adaptations for socioeconomic status and urban settings such as living in multi-generational households, living in apartments and small spaces that required creating separate zones within one room, potential inability to regulate room temperatures, and limited control of noise or light pollution, as well as adaptations to sleep hygiene guidelines for safety concerns. Other important adaptations that were made were related to the salience of immigrant identity, country of origin/heritage group, the importance of family, and adaptations for health literacy and numeracy.

4.4 END-OF-STUDY DEFINITION

A participant is considered to have completed the study if he or she has completed the baseline assessment, at least 4 intervention sessions, and the 6-month follow-up assessments.

The end of the study is defined as completion of the 6-month follow-up assessment shown in the Schedule of Activities (SoA), **Section 1.3**.

5 STUDY POPULATION

5.1 INCLUSION CRITERIA

In order to be eligible to participate in this study, an individual must meet all of the following criteria:

- 1. Provision of signed and dated informed screening consent form
- Stated willingness to comply with all study procedures and lifestyle considerations (see Section 5.3, Lifestyle Considerations) and availability for the duration of the study (8 months)
- 3. Males and females; Age 18-65
- 4. Adults with moderate insomnia symptoms as documented on initial eligibility screen based on validated cut-off for community samples (Insomnia Severity Index Score >10)
- 5. Willingness to adhere to the digital therapeutic treatment (study-app based intervention) or enhanced usual care study regimen
- 6. Be Spanish-speaking or bilingual (English and Spanish) adults
- 7. Self-identify as Hispanic or Latinx
- 8. Report experience of sleep disturbances for at least 3x/week
- 9. Report experience of sleep disturbances for at least 3 months

5.2 EXCLUSION CRITERIA

An individual who meets any of the following criteria will be excluded from participation in this study:

- 1. Participants who are pregnant
- 2. Participants who are caregivers (e.g., mothers or fathers) of infants (< 3 months of age) or of adults who require care at night
- Participants who are deemed unable to complete the study protocol as a result of cognitive impairment, severe medical (i.e., unstable epilepsy or seizure disorder, treatment for cancer or congestive heart failure, or a condition that may require hospitalizations, surgery, or new treatments during the study period) or severe mental illness (schizophrenia, psychosis, bipolar I disorder), or active substance use disorder
- 4. Participation in another treatment or intervention study that would interfere with the current study within the time period beginning from initial baseline assessment until the 6-month follow-up assessment
- 5. Participation in regular night shift work more than 1x/ week
- 6. Patients with severe excessive daytime sleepiness ESS>=16
- 7. Patients with self-reported previous diagnosis of untreated moderate-to-severe obstructive sleep apnea
- 8. Patients with self-reported or health professional diagnosis of narcolepsy
- 9. Patients who have received specialty behavioral treatment for insomnia within the past 3 months
- 10. Change in prescribed depression medications within the past 3 months
- 11. Change in prescribed insomnia medications (e.g., hypnotics) within the past 1 month, or use of a sedative hypnotic beyond the max therapeutic dose

18 May 2022

- 12. Unavailable for follow-up during the study period (e.g., plan to leave the country for an extended period of time without access to internet)
- 13. Absence of primary care provider consent for patient participation
- 14. Patients with non-standard sleep patterns (bedtimes outside of 8pm-2am or awakenings outside of 4am-10am)
- 15. Patients who have full-time transportation and moving occupations (e.g., full-time motor vehicle operators, drivers [e.g., Ubers, Lyfts, taxis, trucks], pilots)

Children under 18 years will not be included in the study. They will not be included as chronic insomnia is much less common in children than in adults.

5.3 LIFESTYLE CONSIDERATIONS

During this study, participants are asked to:

- Refrain from starting specialty behavioral treatment or pharmacotherapy for insomnia.
- Should not be planning on becoming pregnant in the 8-month duration of the study.
- Remain available during the study period, and as such should refrain from leaving the country for an extended period of time

If a participant has used prohibited medications, if they become pregnant during the study duration, or leave the country for extended periods of time, that will result in early study intervention discontinuation by the study investigator.

5.4 SCREEN FAILURES

Screen failures are defined as participants who consent to participate in this study but are not subsequently assigned to the study intervention or entered in the study. Individuals who do not meet the criteria for participation in this trial (screen failure) because of meeting one or more exclusion criteria that are likely to change over time may be rescreened. Examples include participation in night shift work, pregnancy, change in psychotropic medications for depression in past 3 months or insomnia in past 1 month, caregiving for infant <3 months of age or unavailability during the study period. Rescreened participants will be assigned the same participant number as for the initial screening.

5.5 STRATEGIES FOR RECRUITMENT AND RETENTION

18 May 2022

We will enroll 200 Hispanic/Latinx women and men in equal proportion (50% women, 50% men). Participants will be from several racial groups (27% American Indian, 15% Black or African American, and 58% other races or multiple). Participants will be ages 18-65 years old. Participants will be recruited through flyers, email, telephone, and primary care provider referrals from the primary care clinics affiliated with Columbia University Irving Medical Center and New York Presbyterian Hospital (the Ambulatory Care Network) that serves underserved communities across New York City by providing high quality and affordable patient-centered care. Recruitment will be conducted remotely or in person ensuring safety measures are in line with COVID-19 safety guidelines provided by Centers for Disease Control and Prevention and Columbia School of Social Work. All interested patients will complete a standard insomnia questionnaire (the Insomnia Severity Index) to determine study eligibility according to severity of insomnia, and only those patients with a positive insomnia screen who are eligible to participate will be invited for **a remote** study visit, or an in-person visit dependent on participant preference.

For Spanish-speaking patients: We also have developed a range of strategies aimed at racial/ethnic minority patient populations from which we recruit and consent. In particular, we are sensitive to the cultural diversity of our population and appreciative of language barriers, issues that must be addressed for successful recruitment and retention of participants. To accommodate the Hispanic/Latinx community in New York City and the surrounding boroughs, the consent and research participant forms will be in Spanish and written at a 6th grade reading level to ensure suitability across literacy levels. In addition, our hiring practices have been informed by the needs of our population. For our current studies, approximately 75% of our research staff is bilingual and we intend to keep our proportion of Spanish speaking staff at about the same proportion in this project. Hispanic/Latinx participants will be provided with a copy of the consent form and HIPAA form in Spanish. A verbal explanation by a bilingual research member will be provided as well. All ensuing questions will be answered, and participants will then be allowed to sign the consent form and HIPAA form.

Participant incentives

There are no direct benefits to completing the screener. All adult participants have the opportunity to receive up to \$180 for their participation depending on which study group they are assigned to. Participants will be informed that they are able to stop participation at any time. The participant incentives are consistent with going rate for study participation in NYC and are not viewed as coercive.

- A. Somryst Treatment Group (up to \$180 total):
 - 1. \$20 in cash/giftcard for completing the baseline visit
 - 2. \$20 giftcard for wearing the Actiwatch and completing sleep diaries for 14 days at the group assignment visit.
 - 3. \$20 for wearing the Actiwatch and completing sleep diaries for 14 days after treatment is complete.
 - 4. \$40 giftcard for a the post-intervention (9 weeks) telephone call.

18 May 2022

- 5. \$80 giftcard for a 6-month telephone call.
- B. Minimally enhanced usual care (up to \$180 total):
 - 1. \$20 in cash/giftcard for completing the baseline visit
 - 2. \$20 giftcard for wearing the Actiwatch and completing sleep diaries for 14 days at the group assignment visit.
 - 3. \$20 giftcard for wearing the Actiwatch and completing sleep diaries for 14 days after treatment is complete.
 - 4. \$40 giftcard for a post-intervention (9 weeks) telephone call.
 - 5. \$80 giftcard for a 6-month telephone call.

6 STUDY INTERVENTION(S) OR EXPERIMENTAL MANIPULATION(S)

6.1 STUDY INTERVENTION(S) OR EXPERIMENTAL MANIPULATION(S) ADMINISTRATION

6.1.1 STUDY INTERVENTION OR EXPERIMENTAL MANIPULATION DESCRIPTION

Intervention Arm: digital CBT-I (Somryst), usual care, and sleep hygiene brochure.

Patients who are randomized to Somryst will receive the Spanish-language version of the culturally adapted Somryst, a self-guided digital program of CBT-I, the usual care provided by their PCP, and a sleep hygiene brochure. Somryst, is an interactive and tailored mobile-based program modeled on the primary tenets of face-to-face CBT-I, the web version has been shown to be effective at reducing insomnia symptoms.^{25,26}

Patients will be asked to complete six cores (main intervention content) during the 9-week intervention period (a new Core becomes available 7 days after completion of the previous one). After completing a Core, they can review that Core at any time, and access program worksheets from the My Stuff section of the mobile program (App).

The six cores are based on the primary treatment components provided in face-to-face cognitive behavioral therapy for insomnia.^{6,14} The Behavioral Cores incorporate sleep restriction and stimulus control, providing patients with a variety of "rules" to follow in order to retrain their bodies to associate sleep with bed. Stimulus control aims to reduce the anxiety or conditioned arousal individuals may feel when attempting to go to bed. Sleep restriction is a form of systematic mild sleep deprivation in which a sleep window is maintained to allow the body to relearn proper sleeping dynamics and increase sleep efficiency. The Educational Core (also called Sleep Hygiene) focuses on general education about sleep (e.g., understanding the different types of sleep problems) and improving sleep hygiene and other maladaptive behaviors (e.g., establishing regular sleeping schedules, eliminating napping, and avoiding nicotine, caffeine, exercise, and drinking alcohol before bedtime). The Cognitive Core (also called Cognitive Restructuring) attempts to address and change the negative beliefs and thoughts about sleep

18 May 2022

that may exacerbate sleep difficulties. In addition to these main Cores, there are two other Cores: the Overview and Consolidation/Relapse Prevention Cores. These are critical for each user to receive in order to introduce intervention content and provide a rationale for the intervention (Overview); and integrate the educational, behavioral, and cognitive elements, promote adherence, generalize the information, help the user identify risk situations, and incorporate strategies to reduce relapse (Relapse Prevention).

Somryst relies on user-entered online Sleep Diaries to track progress and to tailor treatment recommendations (i.e., assign a "sleep restriction" window). Intervention content is enhanced through a variety of interactive features, including personalized goal-setting, graphical feedback based on inputted symptoms, animations/illustrations to enhance comprehension, quizzes to test user knowledge, patient vignettes, and video-based expert explanation.

The primary outcome, insomnia symptoms, will be assessed using the ISI at baseline, at post-intervention (9 weeks), and at a 6-month follow-up. Health-related quality of life, sleep quality, secondary outcomes, will also be assessed at the same endpoints as ISI. Daytime sleepiness, another secondary outcome will also be assessed at baseline and at the post-intervention (9 weeks), and 6-month follow-up visit. Satisfaction with care and sleep quality will be assessed at baseline and at post-intervention (9 weeks) and 6-months, and sleep duration and efficiency will be assessed 14 days prior to randomization and at post-intervention (9 -weeks).

Comparator Arm: minimally Enhanced Usual Care (mEUC)- (usual care + sleep hygiene brochure) Patients randomized to the mEUC condition will continue to receive the typical standard of care in that clinic from their primary care provider (which may include pharmacotherapy). We have labeled the condition "minimally enhanced" because patients will be provided with a sleep hygiene brochure. Minimally EUC was chosen as the comparator because it is of high clinical relevance, will allow us to determine if the adapted digital CBT-I is superior to usual care, and addresses ethical issues (i.e., identifying but not treating insomnia).⁷⁸ Patients randomized to mEUC will complete assessments on the same schedule as those randomized to the intervention arm.

6.1.2 ADMINISTRATION AND/OR DOSING

Somryst is self-guided as it is a mobile or digital program. Intervention content is metered out over time through 6 "Cores:" psychoeducation, sleep restriction, stimulus control, cognitive restructuring, sleep hygiene, and relapse prevention. Users obtain access to a new Core 7 days after completion of previous Core. Participants will complete the program in 6-9 weeks. A Core is expected to take 45 – 60 minutes to review online. Reviewing and implementing program recommendations will take most participants 30 – 45 minutes per week. Thus, in total, participants in the Somryst group should expect a time commitment of up to 12 hours, total. Somryst relies on user-entered online daily Sleep Diaries to track progress and to tailor treatment recommendations (i.e., assign a "sleep restriction" window). A complete dose is considered completion of 6 cores. We will also collect information about number of sleep diaries completed, number of notifications sent, number of days to complete intervention.

6.2 FIDELITY

18 May 2022

6.2.1 INTERVENTIONIST TRAINING AND TRACKING

Because Somryst is self-guided and delivered completely via mobile App, fidelity to the intervention content will be 100% since there are no interventionists. Study personnel will train participants on the use of Somryst via a virtual Zoom meeting at the randomization visit. A checklist for the training session will be developed for study personnel which will include a standard set of app functions to review such as how to sign on and off of the app, how to navigate the app, and where to find help information on the app. Study videos related to downloading the app and completing sleep diaries will be available to participants and posted on the study website.

Protocol compliance will be reviewed during weekly meetings between [name], TBN (Project Coordinator) and the research assistants, as well as at monthly meetings (more frequent if required) between [name] and the other co-Is (Drs. [name], [name], [name]). Finally, the Project Coordinator will perform a random audit of 5% of study visits, and provide continual feedback to improve the quality of informed consent and data collection.

We have a number of strategies to ensure the quality of the data. First, the web-based electronic data entry system we will use "forces" responses to most questionnaire items before allowing progression through the particular interview's template, thereby avoiding problems with missing data. For some items, delayed data entry is possible. Further, each time the research coordinator logs into the secure data entry system, it prompts pop up on the initial screen showing what data elements remain incomplete, to encourage complete data capture. After enrollment of the first 5 participants, the Steering Committee, led by PI [name] will examine the data to ensure adequacy and accuracy of data collection. Finally, as mentioned above, the DSMB will also review data completeness, accuracy, and timeliness.

6.3 MEASURES TO MINIMIZE BIAS: RANDOMIZATION AND BLINDING

Randomization. After completing the baseline assessment, patients will be randomly assigned in a 1:1 ratio to either the Culturally Adapted Somryst or minimally Enhanced Usual Care (mEUC) condition. Randomization will be generated by a computerized random-number sequence programmed by the study statistician and implemented in the secure, password-protected, encrypted data tracking program. The sequence will be unknown to research assistants enrolling patients.

Blinding. One research staff member (TBN) will be responsible for randomizing participants and so this research assistant and the PI will be unblinded to study condition. Participants will also be unblinded to study condition since treatment conditions will be obvious to them. Research assistants conducting the post-intervention (9 weeks) and 6-month outcome assessments will be blinded to participants' treatment condition, as this is preferred to minimize risk of bias in outcome ascertainment.

6.4 STUDY INTERVENTION/EXPERIMENTAL MANIPULATION ADHERENCE

18 May 2022

Participants will be asked to complete daily sleep diaries and weekly Cores (6 total) over a 9-week (63 days) period. Research staff will receive weekly information about participant engagement with the digital treatment, including number of log-ins, number of minutes to complete core, number of sleep diaries completed, and time elapsed since completion of core. In the event that participants have not started the App, a notification reminder is sent every day for 8 days. Also, periodic notifications are sent after a set period of non-activity. Please see Appendix of Administrative forms for example notification log.

6.5 CONCOMITANT THERAPY

For this protocol, participants may not begin any specialized behavioral treatment or pharmacotherapy for insomnia for the duration of the study.

6.5.1 RESCUE THERAPY

N/A

7 STUDY INTERVENTION/EXPERIMENTAL MANIPULATION DISCONTINUATION AND PARTICIPANT DISCONTINUATION/WITHDRAWAL

7.1 DISCONTINUATION OF STUDY INTERVENTION/EXPERIMENTAL MANIPULATION

When a participant discontinues from Somryst but not from the study, remaining study procedures will be completed as indicated by the study protocol. If a clinically significant finding is identified (including, but not limited to changes from baseline) after enrollment, the investigator or qualified designee will determine if any change in participant management is needed. Any new clinically relevant finding will be reported as an adverse event (AE).

The data to be collected at the time of study intervention discontinuation will include the following:

- The reason(s) for discontinuing the participant from the intervention, and methods for determining the need to discontinue
- If the participant is due to complete assessments within 2 weeks of being discontinued from the study intervention, those assessments will be administered at the time of discontinuation; if the next scheduled assessments are more than 2 weeks from the discontinuation date, the discontinued participant will wait for the next scheduled assessment. Thereafter, the participant will be included in all future scheduled assessments, even though not participating in the intervention.

18 May 2022

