7.3 LOST TO FOLLOW-UP

A participant will be considered lost to follow-up if he or she fails to return for 3 scheduled visits and study staff are unable to contact the participant after at least 3 attempts.

The following actions must be taken if a participant fails to return to the clinic/virtual meeting for a required study visit:

- The site will attempt to contact the participant, reschedule the missed visit within 14 days, counsel the participant on the importance of maintaining the assigned visit schedule and ascertain if the participant wishes to and/or should continue in the study
- Before a participant is deemed lost to follow-up, the investigator or designee will make every effort to regain contact with the participant (where possible, 3 telephone calls and texts, if necessary, a certified letter to the participant's last known mailing address, email, or local equivalent methods). These contact attempts will be documented in the participant's study file.

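### Section 7.1 lets the 9-week ISI be taken up to 2 weeks early for participants who stop Somryst, with no matching rule for mEUC, so primary-outcome timing can depend on arm

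*Combined protocol and SAP*

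**What the plan says.** Section 7.1 deals with participants who leave the program but stay in the trial: "When a participant discontinues from Somryst but not from the study, remaining study procedures will be completed as indicated by the study protocol". It then makes timing depend on how close the next assessment is. If one is due within 2 weeks of stopping, "those assessments will be administered at the time of discontinuation". If it is further off, "the discontinued participant will wait for the next scheduled assessment". After that the participant rejoins the later scheduled assessments. The intervention period is 9 weeks (Section 6.1.1), so the 9-week visit is the one this rule mainly reaches.

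Section 6.1.1 says of the control arm: "Patients randomized to mEUC will complete assessments on the same schedule as those randomized to the intervention arm". It describes that arm's care as follows: "Patients randomized to the mEUC condition will continue to receive the typical standard of care in that clinic from their primary care provider". A sleep hygiene brochure is added. There is no program to leave.

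Section 9.4.2 fits Time as three nominal visits. Assessment date is not in the model, and the post-intervention contrast is tested first. No timing sensitivity analysis is planned. Section 8.1 gives the ISI a 2-week recall period.

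**The concern.** Whether a patient's first primary-outcome value is taken on time can depend on an event after randomization, namely stopping the program, and the rule is written for one arm only. With a 2-week recall, an ISI taken at week 7 describes weeks 5 to 7, yet it would be compared with mEUC values describing weeks 7 to 9. Nothing later in the plan corrects for this.

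Section 7.1 also does not say whether the early ISI replaces the scheduled one. The return to later assessments reads as though it does. If it does not, such a patient has two candidate values and the plan does not say which is analysed.

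At stake is a 9-week contrast that is not measured at the same time in both arms, under a plan that commits to intent-to-treat (Section 9.3).

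**Working it through.** **Inputs from Section 9.2.** Difference 3 ISI points; SD of change 6.0; 200 randomized 1:1; 15% attrition, leaving 170 (85 per arm); expected improvement 8 points on Somryst and 5 on mEUC. Section 9.4.2 gives two-sided alpha 0.05. Section 7.1 gives a maximum shift of 2 weeks.

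**Inputs the documents do not give, so assumed.** The share f of analysed Somryst patients who stop in the last 2 weeks before the visit, and how the ISI moves after stopping.

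**Step 1: the plan's own power.** SE = 6 × √(2/85) = 0.920. Power = Φ(3/0.920 − 1.96) = 90.3%. The stated 90% reproduces.

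**Step 2: error in the contrast.** If only Somryst values are shifted, error = f × mean weeks shifted × ISI change per week between the early date and week 9. Even accrual gives 8/9 = 0.89 point per week at the Somryst rate and 5/9 = 0.56 at the mEUC rate. Two weeks is the largest possible shift; if stopping is spread evenly over the window, the mean is 1 week.

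**Step 3: results if patients are still improving.** The effect is then understated, and power = Φ((3 − error)/0.920 − 1.96).

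| f | Mean 1 week, 8/9 per week | Full 2 weeks, 8/9 per week | Mean 1 week, 5/9 per week |
|---|---|---|---|
| 5% | 0.04 points; 89.5% | 0.09; 88.6% | 0.03; 89.8% |
| 10% | 0.09; 88.6% | 0.18; 86.6% | 0.06; 89.2% |
| 20% | 0.18; 86.6% | 0.36; 81.9% | 0.11; 88.1% |

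**Step 4: what a larger error would take.** For 0.3 points, a tenth of the planned effect, f must be 0.3/(2 × 8/9) = 17% with every shift at the maximum, or 0.3/(8/9) = 34% with a mean 1-week shift.

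**Step 5: direction.** The error is the gap between the early score and the score the same patient would have had at week 9. If patients plateau after stopping, the gap is zero. If they worsen, the early score flatters Somryst and the sign reverses. For example, 0.09 points in that direction would raise the chance of rejection to 91.9%.

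**The case against.** The strongest reply is that this is an ordinary exception to a general schedule, that it protects outcome capture, and that its effect is negligible. Much of that stands.

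- **Size.** The 8/9 slope is the on-treatment rate for the whole arm, applied to people who have left treatment. Nothing in the documents supports it for them, and the stopping share is assumed. The program takes 6 to 9 weeks (Section 6.1.2), so some patients will have finished before the window opens. The 15% in Section 9.2 covers all attrition.
- **Data capture.** Assessing a departing participant while in contact can save a value that would otherwise be lost. Section 9.4.2 commits to seeking outcomes after dropout from the intervention. This is a good reason not to remove the early assessment altogether.
- **Other timing variation.** Section 7.3 tells staff to "reschedule the missed visit within 14 days", in either arm. That moves visits later and is not tied to stopping treatment, so it does not offset a forward shift in one arm.

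A reader might go further and infer four things that the documents do not support:

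- **That the rule does bias the result against Somryst, by up to 0.36 points.** That figure needs a 20% stopping share, the maximum shift for every stopper, and continued improvement at the on-treatment rate.
- **That mEUC values cannot be shifted.** This is inferred from silence. Section 5.3 words its consequence for any participant: "that will result in early study intervention discontinuation by the study investigator". Voluntary stopping of a program still exists only in Somryst.
- **That the early value is taken mid-course.** By construction the patient has already stopped.
- **That the 14-day actigraphy and diary window moves with the ISI.** Section 7.1 does not mention it, and a 14-day recording cannot be administered on one day.

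**Conclusion.** The point holds as a weakness in outcome timing. Section 7.1 permits an early 9-week ISI for Somryst stoppers, no mEUC counterpart is written, Section 6.1.1 promises a common schedule, and the model ignores actual dates. The rule can therefore bias the primary contrast.

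The bias is probably small: about 0.04 to 0.18 of 3 points for stopping shares of 5% to 20%, with power of 89.5% to 86.6% against 90.3%. This rests on a mean 1-week shift and linear accrual at 8/9 point per week. A full 2-week shift doubles the error and is the upper value under that slope. The stopping share, the slope and the sign are not in the documents, so the figures illustrate scale and are not estimates. Because the sign is unknown, the rule could not be defended afterwards as conservative. The remedy is cheap and the change is worth making, but the finding does not undermine the design or the sample size.

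**What to change.** Reconcile Sections 7.1 and 6.1.1 on outcome timing:

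- Assess every participant in both arms at the scheduled 9 weeks and 6 months, whether or not Somryst was stopped, and name the scheduled value as the one analysed.
- Allow an ISI taken at discontinuation only as an additional value, or as a backup when the scheduled one cannot be obtained.
- Record the actual date of every assessment.
- Add to Section 9.4.2 a sensitivity analysis that excludes early values.

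This concerns measurement only and leaves the grounds for stopping treatment untouched. It takes an edit to one bullet and a short addition to the analysis section; the sample size is unchanged. The downside is one extra contact for a few stoppers, some of whom may be harder to reach 1 to 2 weeks later. The backup value limits that loss.
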